6.3.1.1 Optional dose tapering strategy for INC424 in the event of discontinuation

When INC424 therapy is stopped, return of constitutional symptoms associated with elevated cytokines (e.g. night sweats, fever, fatigue) that had been suppressed while on therapy is expected. When a decision is made to permanently discontinue INC424 therapy for reasons other than for hematologic safety, a dose tapering strategy may be considered, based on evaluation of the condition of the patient, current dosing regimen and the clinical judgment of the Investigator, so that symptoms may return to pre-treatment condition more slowly. If considered to be medically necessary, the Investigator may use any treatment to manage withdrawal from INC424 including a gradual tapering of the study drug dosage or use of other medications to manage events occurring after discontinuation. Short-term courses of corticosteroids at doses > 10 mg/day have been used in patients with MF and may be considered as part of a tapering strategy. Corticosteroids may be started prior to, or concurrent with, INC424 tapering. When a decision has been made to discontinue the patient with utilization of a tapering strategy, regardless of the use of concomitant medications, safety data will continue to be assessed in accordance with the protocol for a period of time as least through the continued administration on INC424 and 30 days after for AEs.

6.3.2 Follow-up for toxicities

Patients whose treatment is interrupted or permanently discontinued due to an adverse event or clinically significant laboratory value, must be followed up at least once a week (or more

frequently if required by institutional practices, or if clinically indicated) for 4 weeks, and subsequently at approximately 4-week intervals, until resolution or stabilization of the event, whichever comes first. Appropriate clinical specialists should be consulted as deemed necessary. Further guidelines and recommendations for the management of specific study drug combination induced toxicities (thrombocytopenia and neutropenia) are provided in [Section 6.3.2.1](#) and [Section 6.3.2.2](#). All patients must be followed up for adverse events and serious adverse events for 30 days following the last dose of LDE225 and/or INC424.

Table 6-7 Follow-up evaluations for selected toxicities

| Toxicity | Follow-Up Evaluation |
|----------------|--|
| Hematology | If any hematological DLT has occurred, the relevant parameters must be repeated at least twice a week until resolution to \leq CTCAE grade 1, and then at least weekly until either initiation of treatment or until stabilization. |
| Renal | If any renal DLT has occurred, the relevant parameters must be repeated at least twice a week until resolution to \leq CTCAE grade 1 or baseline, and then at least weekly until either initiation of re-treatment or until stabilization. |
| Hepatic | If any hepatic DLT has occurred, the relevant parameters must be repeated at least twice a week until resolution to \leq CTCAE grade 1 or baseline, and then at least weekly until either initiation of re-treatment or until stabilization. Patients with total bilirubin $>$ ULN (any duration) should have fractionation of bilirubin into total/direct or indirect/direct components and any additional assessments as clinically indicated by these results. |
| Non-laboratory | Patients who experience non-laboratory DLTs must be evaluated at least once a week following demonstration of the toxicity until resolution of the toxicity, to allow for retreatment, until stabilization of the toxicity, or EOT. |
| Cardiac | If \geq grade 3 (QTcF $>$ 500 msec as identified by the investigator on the ECG reading or $>$ 60 ms change from baseline on at least 2 separate ECGs taken within 1 hour): The patient must be hospitalized or monitored by the investigators with hourly ECGs until the QTcF is \leq 500 msec and $<$ 30 msec from baseline. Immediate attention to potassium and magnesium and other clinical factors such as oxygenation, ischemia, and the like will be addressed. A plasma sample should be drawn to assess the concentration of LDE225, magnesium and potassium at the time when the absolute QTcF $>$ 500 msec. Once QTcF prolongation has resolved, reinstate treatment according to Table 6-4 and perform ECG monitoring weekly. If the ECGs obtained in the first 6 weeks after dose reduction are without any QTcF $>$ 500 msec and QTcF change from baseline \geq 60 msec, then ECG monitoring should be performed every 4 weeks. |

[figure not shown]
6.3.2.1 Management of thrombocytopenia

It is recommended that patients who are dose reduced for thrombocytopenia have more frequent hematology assessments. Platelet counts must be obtained at least weekly for 4 weeks, and then at least every second week for the next 4 weeks. Thereafter, they may resume normal scheduled evaluations.

Dose escalation guidelines which allow maximum doses for patients who have previously decreased dosing for thrombocytopenia are described in [Table 6-6](#).

In the case of grade 4 thrombocytopenia, assessment of platelet count is recommended to be repeated twice weekly, until resolution to grade \leq 3 thrombocytopenia.

Dose restart guidelines and allowed maximum doses for patients who have previously interrupted dose for grade 4 thrombocytopenia can be found in [Table 6-6](#).

6.3.2.2 Management of neutropenia

In the case of grade 4 neutropenia, assessment of ANC count is recommended to be repeated at least twice a week until resolution to grade ≤ 3 neutropenia.

Dose restart guidelines and allowed maximum doses for patients who have previously interrupted dose for grade 4 neutropenia can be found in [Table 6-6](#).

6.3.3 Anticipated risks and safety concerns of the study drug

Appropriate eligibility criteria and specific DLT definitions, as well as specific dose modification and stopping rules are included in this protocol. Refer to preclinical toxicity and or clinical data found in the [LDE225 and INC424 Investigator's Brochures].

6.4 Concomitant medications

6.4.1 Permitted concomitant therapy

The patient must be told to notify the investigational site about any new medications he/she takes after the start of the study drug. All medications (other than study drug) and significant non-drug therapies (including physical therapy and herbal/natural medications) administered during the study must be listed on the Concomitant Medications or the Surgical and Medical procedures eCRF. Blood Transfusions will be recorded on the Blood component transfusion eCRFs.

6.4.2 Permitted concomitant therapy requiring caution and/or action

Patients receiving these medications listed below must be monitored closely for any potentiation of toxicity or decrease of clinical benefit due to any individual concomitant medications, and may require dose adjustment.

6.4.2.1 Breast cancer resistance protein (BCRP)

LDE225 is an inhibitor of breast cancer resistance protein (BCRP) *in vitro*. Therefore substrates, especially those with a narrow therapeutic range, should be used with caution. BCRP substrates include zidovudine, pantoprazole, cimetidine, sulfasalazine, nitrofurantoin, mitoxantrone, methotrexate, topotecan, imatinib, and irinotecan. However, the use of mitoxantrone, methotrexate, topotecan, imatinib, irinotecan or statins is generally prohibited during this study (see [Appendix 1](#); [Table 14-1](#)).

6.4.2.2 Drugs that are metabolized by or affect CYP450 enzymes

In vitro drug metabolism studies suggest that the metabolism of LDE225 and INC424 are both primarily mediated by CYP3A4. Therefore, caution is advised for co-administration of drugs that are weak inhibitors or inducers of CYP3A4 ([Appendix 1](#); [Table 14-2](#)). Concomitant treatment with weak inducers of CYP3A4 is permitted, however, duration of concomitant treatment should be kept as short as possible (e.g, less than 1 week), or fully avoided whenever possible. Weak inducers include, but are not limited to armodafinil, nevirapine, oxcarbazepine, pioglitazone, pleconaril, rufinamide and troglitazone. Note that

coadministration of study drug with strong and moderate CYP3A inducers ([Appendix 1](#)) is prohibited.

LDE225 was shown to inhibit CYP2B6 and CYP2C9 *in vitro*, therefore, CYP2B6 and CYP2C9 substrates should be used in caution. Refer to [Table 14-3](#) in [Appendix 1](#) for a list of CYP2B6 and CYP2C9 substrates to be used with caution. Narrow therapeutic index or sensitive substrates of CYP2B6 and CYP2C9 are not permitted (refer to the prohibited section below).

6.4.2.3 Corticosteroids

Chronic dosing of corticosteroids (e.g. dexamethasone and prednisone) is known to induce CYP3A enzymes, thereby increasing the risk of reducing drug exposure to sub-therapeutic levels. Systemic corticosteroid doses greater than the equivalent of 10 mg of prednisolone per day are not permitted, unless its use is part of a INC424 dose tapering strategy ([Section 6.3.1.1](#)) as this may impact splenic size and cytokine reduction and interfere with the ability to assess the clinical activity of this drug treatment combination in this patient population. Stable corticosteroids used for conditions other than MF are allowed if the doses are less than the equivalent of 10 mg of prednisolone per day during the course of the study but the dose must have been stabilized (or decreasing) for at least 5 days before initiating study therapy and any ongoing corticosteroid use during study treatment must be clearly documented on the concomitant medication eCRF.

6.4.2.4 Permitted antifungal and antibiotic medications

Permitted antifungal and antibiotic agents, including those that are weak inhibitors or inducers of CYP3A4 are listed in [Appendix 1](#), [Table 14-4](#). Topical and vaginal antifungals are generally allowed with caution.

6.4.2.5 Hematopoietic growth factors

Therapeutic use of hematopoietic growth factors is allowed according to institutional guidelines. Granulocyte growth factors (G-CSF) are not allowed while study medication is being administered but may be used for severe neutropenia at the Investigator's discretion while study medication is being withheld.

6.4.3 Prohibited concomitant therapy

The following medications have restrictions on their use and may require changes in dosing when INC424 and/or LDE225 are administered during the study. Refer to [Appendix 1](#) for a list of prohibited medications. This list may not be comprehensive.

6.4.3.1 Other investigational therapies

Use of any other investigational medication (other than LDE225 and INC424) that is not approved for any indication is not allowed. Use of such medications within 30 days, prior to the first dose of study drug and during the study through the Safety Follow-up Visit is prohibited. Anticancer therapy (chemotherapy, biologic or radiation therapy, and surgery) other than the study treatments (LDE225 and INC424) must not be given to patients while the

patient is on the study medication. If such agents are required for a patient then the patient must be discontinued from the treatment portion of the study.

6.4.3.2 Strong and moderate CYP3A4 inhibitors and inducers

In vitro drug metabolism studies suggest that the metabolism of LDE225 and INC424 are both primarily mediated by CYP3A4. Co-administration with strong and moderate CYP3A4 inhibitors and inducers is predicted to respectively increase or decrease the systemic exposure to the study drugs ([Appendix 1](#); [Table 14-5](#)), and is therefore prohibited.

6.4.3.3 Narrow therapeutic index or sensitive substrates of CYP2C9 and CYP2B6

Because of the potential risk for drug-drug interactions with LDE225, using concomitant medications known to be metabolized by the cytochromes CYP2C9 and CYP2B6 that have low therapeutic index is not permitted in the study ([Appendix 1](#); [Table 14-6](#)). In the absence of clinical drug interaction data, therapeutic doses of warfarin or any other Coumadin-derivative anticoagulants are not permitted since LDE225 is a competitive inhibitor of CYP2C9 based on the *in vitro* data.

6.4.3.4 Drugs that interfere with coagulation or inhibit platelet function

Drugs that interfere with coagulation or inhibit platelet function (including non-steroidal anti-inflammatory drugs) are not permitted. Aspirin (≤ 150 mg/day) and LMWH (INR less than 1.5) are allowed.

Any other medication for the treatment of myelofibrosis, including but not limited to: hydroxyurea, busulfan, interferon, lenalidomide, thalidomide, anagrelide **are prohibited**.

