 - If a patient cannot tolerate dose level (-1), which is the lowest acceptable dosing level for this study, except for patients in Cohort 1 who experience thrombocytopenic DLTs and can receive INC424 5mg BID and LDE225 200mg QD.
- Disease Progression
- Use of prohibited treatments (refer to Appendix 1) as determined by Novartis
- Use of another myeloproliferative neoplasm directed therapy
- Any other protocol deviation that results in a significant risk to the patient's safety
- Study is terminated by the Sponsor

Patients who discontinue study treatment should NOT be considered withdrawn from the study. They should return for the assessments indicated in [Table 7-1](#) and [Table 7-2](#). If they fail to return for these assessments for unknown reasons, every effort (e.g. telephone, email, letter) should be made to contact them as specified in [Section 7.1.5](#).

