14.1.1 Concomitant medications requiring caution

Table 14-1 Medications that are known substrates of BCRP to be used with caution

| BCRP substrates | | | |
|------------------------|--------------|---------------|------------|
| Nitrofurantoin | Pantoprazole | sulfasalazine | zidovudine |

Table 14-2 List of weak CYP3A inducers or inhibitors to be used with caution

| Weak CYP3A inducers | | | |
|--|----------------------|-------------------------|---|
| armodafinil (R-modafinil) | bexarotene | clobazam | danshen |
| dexamethasone | Echinacea | garlic (allium sativum) | glycyrrhizin |
| methylprednisolone | nevirapine | oxcarbazepine | pioglitazone |
| pleconaril (not available in US market) | prednisone | primidone | raltegravir |
| rufinamide | terbinafine | topiramate | troglitazone (not available in US market) |
| Weak CYP3A inhibitors | | | |
| alprazolam | amlodipine | azithromycin | bicalutamide |
| chlorzoxazone | cilostazol | clotrimazole | cranberry juice |
| cyclosporine | delavirdine | drosiprenone | ethinyl estradiol |
| fluvoxamine | fosaprepitant | isoniazid | lacidipine |
| linagliptin | norgestimate | peppermint oil | pravastatin* |
| propiverine | ranitidine | ranolazine | resveratrol |
| roxithromycin (not available in US market) | seville orange juice | sitaxentan | tabimorelin |
| tacrolimus | tolvaptan | | |

*If it is essential that the patient takes a statin to control hyperlipidemia, then only pravastatin may be used with extra caution.

Table 14-3 List of CYP2B6 and 2C9 substrates to be used with caution

| CYP2B6 substrates | | | |
|--------------------------|------------------|--------------|-------------|
| bupropion | | | |
| CYP2C9 substrates | | | |
| celecoxib | diclofenac | flurbiprofen | glipizide |
| glyburide | gliclazide | glimepiride | lornoxicam |
| indomethacin | irbesartan | ketobemidone | nateglinide |
| losartan | meloxicam | naproxen | piroxicam |
| S-ibuprofen | sulfamethoxazole | tenoxicam | tolbutamide |
| torasemide | valdecoxib | | |

Table 14-4 List of permitted antifungal and antibiotic agents to be used with caution

| Permitted antifungal and antibiotic agents to be used with caution | | | |
|---|---------------|--------------|--|
| amphotericin B | anidulafungin | azithromycin | candididin (not available in US market) |
| caspofungin | clotrimazole | flucytosine | griseofulvin |
| isoniazid | micafungin | nystatin | roxithromycin (not available in US market) |
| terbinafine | | | |

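### NSAIDs are prohibited in Protocol 6.4.3.4, yet Table 14-3 lists eleven of them as usable with caution

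*Protocol*

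**What the plan says.** Protocol 6.4.3.4, one of the prohibited-therapy sections, reads: "Drugs that interfere with coagulation or inhibit platelet function (including non-steroidal anti-inflammatory drugs) are not permitted". It then allows aspirin up to 150 mg/day and LMWH, and nothing else. Exclusion criterion 7 in Protocol 5.3 applies a similar bar at entry to drugs that affect coagulation or platelet function, with the same two exemptions.

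Protocol 6.4.2 is headed "Permitted concomitant therapy requiring caution and/or action". Its opening paragraph asks sites to monitor closely patients who are taking the drugs it covers. Within it, 6.4.2.2 refers the reader to Table 14-3 "for a list of CYP2B6 and CYP2C9 substrates to be used with caution". The table's title is "List of CYP2B6 and 2C9 substrates to be used with caution", and its entries include celecoxib, diclofenac, naproxen and S-ibuprofen.

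Two other statements bear on the point. Section 6.4.3 says of the prohibited list in Appendix 1: "This list may not be comprehensive". Section 7.1.3 gives, as a reason for which study treatment must be discontinued: "Use of prohibited treatments (refer to Appendix 1) as determined by Novartis".

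**The concern.** The body of the protocol bans a drug class, and the appendix lists members of that class as drugs that may be taken with care. A site checking whether a patient may have naproxen is likely to look in the appendix, and there finds it only on a caution list.

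Bleeding safety is the first thing at stake. Patients may enter with platelets as low as 75 x 10^9/L (Protocol 5.2, criterion 5), and counts can fall further on treatment. For Grade 3 thrombocytopenia, 25 to 50 x 10^9/L, Table 6-4 reduces INC424 to 5 mg BID and keeps LDE225 unchanged, so these patients continue on therapy. Demand for analgesics is foreseeable. Bone or muscle pain is one of the MFSAF items (Protocol 7.2.6.1.1), and in the LDE225 phase I study treatment-related muscle spasms were reported in 32.0% of patients and myalgia in 16.5% (Table 1-3). Under Protocol 7.1.3 a Grade 3 or 4 haemorrhage of any kind ends study treatment.

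The second is consistent handling of deviations. SAP 3.2.2 tabulates protocol deviations by category. Whether NSAID use counts as one depends on which of the two places is followed, and the discontinuation rule in 7.1.3 points to the appendix, where NSAIDs appear only as caution drugs.

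**Working it through.** The plan states no figure on this point, so there is nothing to reproduce. The check is a count of table entries and a comparison of the rules.

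**1. CYP2C9 entries in Table 14-3, row by row.** Classing a drug as an NSAID is general pharmacology and is an assumption here.

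| Row | Entries | NSAIDs | Count |
|---|---|---|---|
| 1 | 4 | celecoxib, diclofenac, flurbiprofen | 3 |
| 2 | 4 | lornoxicam | 1 |
| 3 | 4 | indomethacin | 1 |
| 4 | 4 | meloxicam, naproxen, piroxicam | 3 |
| 5 | 4 | S-ibuprofen, tenoxicam | 2 |
| 6 | 2 | valdecoxib | 1 |

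- Entries: 4 + 4 + 4 + 4 + 4 + 2 = 22.
- NSAIDs: 3 + 1 + 1 + 3 + 2 + 1 = 11, so 11 of 22.
- Without the two COX-2-selective agents, celecoxib and valdecoxib: 11 - 2 = 9, so 9 of 22.

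Ketobemidone (row 3) is an opioid and is not counted. Whether meloxicam belongs among the nine is a matter of convention and does not affect the conflict.

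**2. Prohibited tables in 14.1.2.** Tables 14-5 (CYP3A modulators), 14-6 (narrow-index CYP2B6 and CYP2C9 substrates) and 14-7 (antifungals and antibiotics) name no NSAID. This carries little weight by itself, since none of the three is organised around platelet function.

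**3. The two rules side by side.**

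| | 6.4.3.4 | 6.4.2.2 and Table 14-3 |
|---|---|---|
| Heading above it | Prohibited therapy | Permitted therapy needing caution or action |
| NSAIDs | Barred as a class | 11 listed by name for cautious use |
| Exceptions | Aspirin up to 150 mg/day, LMWH | None stated |
| Cross-reference to the other | None | None on NSAIDs |

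**4. Does other text reconcile them?** The caveat in 6.4.3 that the prohibited list may be incomplete explains why a banned drug might be missing from 14.1.2. It does not explain why a banned drug is listed as usable.

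**5. Does the protocol reconcile similar overlaps?** In places it does. Section 6.4.2.1 names 10 BCRP substrates and then says: "However, the use of mitoxantrone, methotrexate, topotecan, imatinib, irinotecan or statins is generally prohibited during this study". All 5 of the named substrates in that sentence are absent from Table 14-1. Cimetidine is absent too, and Table 14-5 prohibits it. That leaves 10 - 5 - 1 = 4 drugs, which is what the table contains. For statins, a footnote to Table 14-2 says: "If it is essential that the patient takes a statin to control hyperlipidemia, then only pravastatin may be used with extra caution". Elsewhere it does not. Table 14-2 lists echinacea, although 6.4.3.6 bars herbal preparations; Seville orange juice, although 6.1.1 tells patients to avoid it; and ethinyl estradiol, although criterion 16 in 5.3 disallows hormonal contraception. A site therefore cannot infer from the appendix which rule takes precedence.

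**6. What is not affected.** Protocol 6.2.5 excludes from the DLT definition events assessed as due to concomitant medication, and the Amendment 2 rationale records the RPIID as confirmed. No effect on the dose-toxicity model is claimed.

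**The case against.** The best counter-reading is that Table 14-3 is a catalogue of metabolic interactions and grants no permission. A drug must satisfy every restriction that applies to it, so a caution about CYP2C9 does not lift a separate ban made on platelet grounds. Where the appendix means permission it says so, as in the title of Table 14-4. The unreconciled entries in Table 14-2 fit this view of the tables, with bans stated in the body text. This is probably what the sponsor intended, but no sentence says it. Section 6.4.2.2 sits under a heading that calls these therapies permitted, and the opening of 6.4.2 tells sites how to monitor patients who take them.

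It can also be said that Table 14-2 shows the protocol reconciling such overlaps only some of the time, so the BCRP and statin examples are selective. That is fair. They show that the protocol can resolve an overlap, not that it always does.

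Third, 7.1.3 leaves the finding of prohibited use to the sponsor, so individual cases have an arbiter. That also stands, but the arbiter acts after the drug has been taken and the text still gives two answers.

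Finally, the reach is limited. Criterion 7 covers entry, the SAP records that Stage 2 will not enrol, and nothing shows that any site misread the rule. What remains is patients already on treatment and in the extension phase. At the Amendment 2 cut-off, 50 patients had been treated and 14 had discontinued, leaving 50 - 14 = 36. In the extension, protocol-scheduled haematology is every 12 weeks (Table 7-2), more often where standard of care requires it.

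**Conclusion.** The contradiction holds as written. Section 6.4.3.4 bans NSAIDs as a class, while a table reached from the permitted-therapy section lists 11 of them among 22 CYP2C9 substrates (9 of 22 without the COX-2-selective agents) as usable with caution, and nothing says which governs. The counts rest on general knowledge of drug class. The documents give no rate of NSAID use or NSAID-related bleeding, so the number of patients affected cannot be stated. No endpoint, estimate or decision rule changes. The consequence is a conflicting instruction on a drug class with bleeding risk, in patients who may stay on treatment at 25 to 50 x 10^9/L platelets, together with inconsistent recording of deviations. It should be corrected.

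**What to change.** Delete the NSAIDs from Table 14-3, or footnote each one there as prohibited under 6.4.3.4, and add NSAIDs to the prohibited list in 14.1.2 so that the reference in 7.1.3 leads to the right answer. If the sponsor's clinical team wants to allow any of them, for example COX-2-selective agents, that exception belongs in 6.4.3.4 next to aspirin and LMWH. The Table 14-2 entries noted above could be checked in the same edit.

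The cost is a change to the appendix tables, plus one sentence in 6.4.3.4 if an exception is wanted. There is no analysis cost.
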